Study protocol

Full title

Human Immune Response Variation in Tuberculosis

Short title

HIRV-TB

Chief Investigator and affiliations

[name], PhD FRCP
Univeristy College London Division of Infection and Immunity,
[name]

Supported by

Wellcome Trust Investigator Award
NIHR Doctoral Research Fellowship

Sponsored by

University College London Hospitals NHS Foundation Trust (UCLH) / University College London (UCL)
(delete as applicable)

Protocol version number and date

Version 2, 14/09/2018

R&D / Sponsor Reference Number(s)

18/0055

IRAS Registration Number:

242062

[figure not shown]
Protocol versions

Version Stage	Versions No	Version Date	Protocol updated & finalised by;	Appendix No detail the reason(s) for the protocol update
Final	2	14/09/2018	[name] (Clinical Research Fellow)	Substantial amendment

Declarations

The undersigned confirm that the following protocol has been agreed and accepted and that the investigator agrees to conduct the study in compliance with the approved protocol and will adhere to the Research Governance Framework 2005 (as amended thereafter), the Trust Data & Information policy, Sponsor and other relevant SOPs and applicable Trust policies and legal frameworks.

I, [name], agree to ensure that the confidential information contained in this document will not be used for any other purposes other than the evaluation or conduct of the clinical investigation without the prior written consent of the Sponsor.

Chief Investigator: [name]	
Signature: 	Date: 14/09/2018
Print Name(in full):	[name]
Position:	Senior Lecturer in Infection and Immunity Honorary Consultant in Infectious Diseases

On behalf of the Study Sponsor:	
Signature: 	Date: 25/9/2018
Print Name(in full):	[name]
Position:	Research Governance Manager

Summary information

IRAS Number	242062
REC Reference No	18/LO/0680
Sponsor Reference No	R&D 18-0005

Full (Scientific) title	Human Immune Response Variation in Tuberculosis	
Health condition(s) or problem(s) studied	Tuberculosis	
Study Type	Observational longitudinal and cross-sectional study	
Target sample size	1000	
Study Duration/length	5 years	
Expected Start Date	1 st June 2018	
End of Study definition and anticipated date	31 st May 2023	
Data and sample storage	Human tissue samples	UCL Division of Infection and Immunity, under custodianship of chief investigator

Appendix 3: Summary of research samples tests at each study visit	19
Appendix 4: Standard operating procedure for TST and biopsies	22
Appendix 5: Participant symptom questionnaire	23

Appendix 6: Study end points.....	24
Appendix 7: Screening and consent log.....	25
Appendix 8: Immunomodulatory drugs.....	26
Appendix 9: Risks to participants	27
Appendix 10: Adverse events.....	29
Appendix 11: Participant case record form	34

1. Introduction

Mycobacterium tuberculosis (Mtb) remains a major threat to global health, causing 10 million new cases of active tuberculosis (TB) disease and 1.8 million deaths per year¹. The prevalence of immunological memory for Mtb, detected by the tuberculin skin test (TST) or by interferon (IFN) γ release assays (IGRA), indicates that many more people experience asymptomatic or latent TB infection (LTBI). Of these, 10% go on to develop active TB²⁻⁵. In the remainder, successful host defence is primarily thought to be mediated by macrophage control of Mtb replication, augmented by IFN γ in T helper (Th)1 responses. The importance of immune defence is further highlighted by Mendelian Susceptibility to Mycobacterial Disease (MSMD) due to inherited deficiencies of IFN γ -associated signalling^{6,7}, and by increased risk of active TB associated with HIV infection⁸ or anti-TNF therapy⁹. Yet, most individuals with active TB have none of these risks, indicating that other variations in immune responses determine outcomes in the majority.

The limitations in our understanding of immune protection against Mtb are a fundamental hurdle to identifying an individual's risk of active disease, and to harnessing the immune system to prevent or treat Mtb infection. On health economic grounds, systematic programs aim to prevent active TB by drug treatment of LTBI, 90% of whom do not need treatment because they will never develop disease^{10,11}. There has been no improvement on the modest efficacy of BCG vaccination¹², and treatment of Mtb infection requires prolonged antimicrobial drugs, increasingly compromised by Mtb drug resistance¹³. Greater understanding of the immune mechanisms that determine the clinical outcome of Mtb infection is a global research priority. These will allow us to target preventative measures at those with the highest risk of active disease. In addition, they will focus attention on immune responses that could be modulated to enhance vaccine efficacy, and to develop host directed therapies in order to reduce the duration of antimicrobial treatment for TB or to mitigate against increasing drug resistance¹⁴⁻¹⁷.

2. Background and rationale

TB disease arises from stochasticity in multivariate immune responses such that variation of any one of many components can tip the balance towards immunological protection or pathogenesis. Genome-wide transcriptional profiling of biopsies from the site of tuberculin skin test (TST) provides comprehensive molecular and systems level assessments of in vivo human immune responses to a standardised mycobacterial challenge, at the site of host-pathogen interactions^{20,21}. This approach allows quantitation of cell-type specific recruitment, Mtb specific innate immune responses and the biological activity of specific cytokines in response to the TST^{20,22,23}, and has been shown to represent variations in molecular pathology at the site of active disease in human TB²⁰.

Transcriptional profiling of TST biopsies in LTBI patients with longitudinal follow up to identify immune response correlates of subsequent progression to active TB. This approach necessitates the ability to exclude active TB in patients at the time of TST challenge, to safely defer LTBI treatment, and to accurately identify individuals progressing to active TB before the onset of clinical disease. Blood transcriptomic biomarkers achieve these aims. They have been shown to accurately discriminate active pulmonary and extrapulmonary TB from LTBI or other infectious diseases²⁴. Blood transcriptomic changes can also predate diagnosis of active disease²⁵. Unpublished data has also shown that blood transcriptional signatures can identify patients who develop symptomatic active TB within 3 months, with positive and negative predictive values of 0.99-1 assuming cumulative 5% pre-test probability of progression to active disease in cohorts of TB contacts^{10,26}.

Twin studies indicate that the risk of active TB has a host genetic component. Candidate gene association studies focussing on innate immune responses have reported putative TB susceptibility loci⁴⁰⁻⁴⁹. Given the complexity of integrated innate and adaptive cell-mediated immunological systems, these studies do not offer the comprehensive approach required to identify the constellation of genetic polymorphisms that may affect TB risk. Conventional genome-wide association studies (GWAS) of active TB have not replicated the findings of candidate gene studies and generally lacked sufficient power⁵⁰⁻⁵⁵. Expression quantitative trait loci (eQTL) studies, in which genome-wide single nucleotide polymorphisms (SNPs) are associated with quantitative differences in transcriptional responses to a stimulus offer substantially greater power to identify the genetic correlates of variation in immune responses⁵⁶⁻⁵⁹. They also provide the fundamental advantage of directly

identifying the functional impact of genetic polymorphisms on both specific molecules and molecular pathways. An eQTL study of TST transcriptional responses offer an important opportunity to identify the genetic correlates of variation in anti-Mtb immune responses.

3. Objectives

3.1. Primary Objective

- Identification of TST immune responses that are associated with increased the risk of active TB.

3.2. Secondary Objectives

- Identification of host-genetic polymorphisms associated with transcriptional variation in the TST.
- In vitro functional validation of eQTL associations and investigation of how they impact on Mtb growth in macrophages.
- To test whether expression of a whole blood transcriptional biomarker for subclinical TB resolves with LTBI therapy (LTBI treatment sub-study).

4. Study design

This is an observational study incorporating longitudinal cohort and cross-sectional components. 400 participants will be recruited to the longitudinal cohort with two year follow up, to identify TST immune responses that increase the risk of active TB (primary objective). Cross-sectional analysis of data from these 400 participants will be combined together with the data obtained from an additional 600 participants, giving a sample size of 1000 recruited over four years in total, to identify host-genetic polymorphisms associated with transcriptional variation in the TST. In vitro functional validation of eQTL associations and investigation of how they impact on Mtb growth in macrophages will be conducted in peripheral blood cells collected from selected participants. Finally, a subset (n=80) of these 1,000 participants who express a blood transcriptional biomarker for subclinical TB will be enrolled in a parallel cohort study, to test whether resolution of biomarker expression is expedited by LTBI therapy. These individuals will be offered treatment for LTBI as per national guidance, but we know that only approximately 40-60% accept this treatment. All patients will be followed up with interval blood sampling. Expression of the 3 gene biomarker will be compared at 4, 8, 12 and 24 weeks between individuals who accept and decline treatment.

5. Study schedule

The longitudinal study will recruit individuals with LTBI from the existing UK contact screening program^{11,27}. The additional individuals for the cross-sectional study will be recruited from the Public Health New migrant screening program referrals to LTBI clinics. Clinical staff at each participating site (Appendix 1) will introduce potentially eligible individuals (Section 7) to the study team, who will seek to obtain informed written consent (see Section 6). The study schedule for participants who give consent is summarised in Appendix 2. They will undergo a chest radiograph (provided by the routine NHS Trust clinical service) and screening blood tests (Appendix 3) and, followed by one tuberculin skin test in each arm. One TST site will be biopsied at 48 hours and the second TST site will be biopsied at seven days (Appendix 4). All blood tests, chest radiography, TSTs and biopsies will be performed within the TB clinic the participant was recruited from.

Participants who have a positive blood transcriptional biomarker will then enter the LTBI treatment sub-study. In the absence of clinical evidence of active TB, they will be offered LTBI therapy as part of their usual NHS care, and asked to attend appointments after 4, 8, 12 and 24 weeks for clinical review and repeat blood sampling (the 4, 8 and 12 week time points are aligned with those required in routine clinical care for monitoring). Adherence to LTBI therapy will be measured by self-report questionnaire, pill counts, urine testing and/or medication boxes, depending on local site availability and practice.

Participants with a negative blood transcriptional biomarker and who meet the eligibility criteria for the longitudinal study will be asked to attend follow up clinic appointments with the study team at three monthly intervals for two years. These additional appointments will take place at the TB clinic the participant was recruited from. At each appointment they will complete a questionnaire (Appendix 5), undergo blood sampling

and a chest radiograph. Participants can withdraw at any time without giving a reason. Participants will also be consented for recall by selected genotype or phenotype to obtain additional peripheral blood samples within the five-year lifetime of this study for in vitro mechanistic studies (see secondary objectives).

Participants who request to withdraw from the study or are lost to follow up will be referred back to the routine clinical service by the study team. Participants who develop a positive blood transcriptional biomarker at any point during longitudinal follow-up will then enter the LTBI treatment sub-study. Participants who develop a positive blood transcriptional biomarker or reach a study end point (Appendix 6) as a surrogate for progressive TB before 2 years, will be identified as progressors. Participants who complete 2 years follow up will be identified as non-progressors. Progressors and non-progressors will undergo routine clinical assessments to evaluate the need for any TB treatment when their participation in the study ends.

6. Recruitment and consent

Potential participants who meet the eligibility criteria will be identified by the routine tuberculosis clinical service and introduced to the study team. The study team will describe the study to these individuals, provide them with the participant information sheet, and answer their questions, in person, by telephone, by post or by email according to the participant's preferences. After at least 24 hours to consider this information, the study team will invite those who agree to participate to provide written informed consent.

For non-English speakers the study team will communicate with telephone translation services and provide translations of the participant information sheet and consent form. The original signed consent form will be filed in the study master file and a copy will be provided to the participant. All participants who are referred to the study team will be entered into a screening log with a record of their eligibility criteria, their decision to participate or reasons for declining to participate as appropriate.

7. Eligibility criteria

7.1. Inclusion Criteria

- Peripheral blood IGRA positive
- Contact of new case of pulmonary tuberculosis (for longitudinal study only)

7.2. Exclusion Criteria

- Age <18 or >60 years
- Unable to give written consent
- Clinical or radiographic features of active tuberculosis
- HIV-1 infection
- Active hepatitis B or C infection
- Pregnancy
- History of autoimmune disease
- History of skin disease
- History of malignancy
- Immunomodulatory drugs (Appendix 6)
- History of allergy to local anaesthetics
- History of keloid scarring

8. Clinical governance and indemnity

The risks for participants in the present study are summarised in Appendix 8.

Participants' General Practitioners will be notified of their patient's involvement in this study, subject to written informed consent by the patient.

All participants will be contacted 1 week after their final visit to check that the TST biopsy wounds have healed as expected. Where necessary, participants will be offered a further appointment for clinical review of the biopsy sites and to instigate appropriate clinical management under the supervision of the Chief Investigator.

Any participants who develop evidence of active tuberculosis will be referred for urgent review by routine clinical TB services.

All adverse events will be recorded as described in Appendix 9. All complaints and adverse events will be reported immediately to the sponsor by email ([contact]) and using the on line incident reporting form (<https://opinio.ucl.ac.uk/s?s=17671>). If the adverse event takes place within a UCLH Trust site, the event will be reported through the Trust incident reporting system (Datix). Annual progress reports will be submitted to the Research Ethics Committee.

University College London holds insurance against claims from participants for harm caused by their participation in this clinical study. Participants may be able to claim compensation if they can prove that UCL has been negligent. However, if this clinical study is being carried out in a hospital, the hospital continues to have a duty of care to the participant of the clinical study. University College London does not accept liability for any breach in the hospital's duty of care, or any negligence on the part of hospital employees. This applies whether the hospital is an NHS Trust or otherwise.

9. Statistical methods

9.1. Sample size and statistical power

We will recruit 400 LTBI contacts of active pulmonary TB cases to address the primary objective. This sample size is derived from estimated progression from LTBI to active TB within 2 years of 5%, giving 20 progressors and 380 non-progressors. Progressive disease may be due to a range of different immune responses, and each variation may only be evident in a subset of cases. Therefore, conventional differential gene expression analysis in the TST between groups of progressors and non-progressors, may not identify statistically significant differences. Instead, we will undertake supervised outlier profile analysis to identify gene expression among subsets of progressors, which lies outside the normal range measured in non-progressors. These methods provide robust statistical confidence by incorporating multiple testing corrections³²⁻³⁶, and have been successfully applied to discovery of novel oncogenic pathways^{32,37}. Using preliminary TST transcriptomic data from HIV negative individuals in computational simulations, we estimate >0.8 statistical power in this sample size to detect significant outlier traits among progressors (false discovery rate <0.05) when the outlier trait is shared by 5 or more progressors (Figure 2A). In order to identify eQTLs of TST transcriptomic data, we estimate that a sample size of 1000 is required to give >90% power to detect statistically significant correlations ($p < 10^{-8}$) for allelic frequencies $\geq 5\%$ depending on the correlation coefficients, as a composite measure of effect size and variance⁶¹. Finally, from our pilot data, we estimate that 15% of these individuals will express the blood transcriptional biomarker at time of recruitment to the study. Of these estimated 150 participants, 80 will be recruited to the LTBI treatment sub-study. Conservatively assuming that only 25% of patients decline LTBI therapy, a sample size of 68 participants will provide 80% power to detect a difference of 0.8 standard deviations (SDs) in signature scores between those who accept and decline treatment at each time point. This calculation assumes similar standard deviations among individuals in both groups. We have estimated 0.8SDs as the minimum difference in signature scores that is likely to be of clinical significance (based on the difference in mean scores between IGRA-positive and IGRA-negative TB case-contacts in our pilot data. To allow for losses to follow-up, 80 participants will be recruited.

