Appendix 9: Risks to participants

Severity score- Low=can cause discomfort but unlikely to have an impact on health, Moderate=potential impact on health but unlikely to be life-threatening, Severe=definite impact on health and significant potential to be life-threatening.

Description of risk	Estimated incident rate	Severity	Justification
Progressive active TB as a result of deferring LTBI treatment in the longitudinal study.	<1%	Moderate	The two year cumulative risk of progressive TB in individuals being recruited to this study (IGRA positive contacts of active pulmonary TB) is estimated to be 5%. In routine clinical practice LTBI treatment is commonly offered to all such individuals. On the basis that this treatment is in fact not necessary for the vast majority, clinical review at 3-6 monthly intervals is widely used as an alternative approach. In the present study, we will undertake enhanced follow up at 3 monthly intervals with the addition of novel blood biomarkers with the potential to identify subclinical active TB representing an end point in their participation, when individuals will be offered treatment in line with standard clinical care. The available data on the predictive value of these biomarkers indicates that this approach minimises the 2 year cumulative risk of the development of symptomatic TB disease <1%. On the basis subclinical active TB will not meet conventional criteria for the diagnosis of symptomatic TB disease requiring full TB treatment, we expect that most participants who develop biomarkers of subclinical TB will be offered LTBI treatment. On the basis of being IGRA positive, all participants who complete 2 year follow up will be considered for LTBI treatment as per routine clinical practice. The risk of active TB is substantially lower after 2 years follow up, therefore these participants may opt not to accept LTBI treatment.

Description of risk	Estimated incident rate	Severity	Justification
Increased radiation exposure due to repeated chest radiographs	100%	Low	Participants may have up to 8 extra chest radiographs. Each of these is equivalent to 10 days of natural background radiation exposure, associated with a negligible additional cancer risk of <0.01%. This risk is substantially outweighed by the benefits of chest radiographic monitoring for evidence of progressive TB.
Discomfort during phlebotomy	10%	Low	The overall risk of harm is very low.

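### Section 9.1 takes its 20 progressors from a 5% active-TB risk for all IGRA-positive contacts, which matches neither the biomarker-negative cohort that is followed nor the protocol's definition of a progressor

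*Protocol*

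**What the plan says.** Protocol Section 9.1 sets the longitudinal sample: "We will recruit 400 LTBI contacts of active pulmonary TB cases to address the primary objective". It then gives the basis: "This sample size is derived from estimated progression from LTBI to active TB within 2 years of 5%, giving 20 progressors and 380 non-progressors". Power above 0.8 at a false discovery rate below 0.05 is claimed on condition that at least 5 progressors share the outlier trait. The claim rests on a simulation whose figure is not available here.

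Appendix 9 states the population behind the 5%: the "two year cumulative risk of progressive TB in individuals being recruited to this study (IGRA positive contacts of active pulmonary TB) is estimated" at that value. It sets no biomarker condition.

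Section 5 splits participants by biomarker at entry. On one side, "Participants who have a positive blood transcriptional biomarker will then enter the LTBI treatment sub-study", where LTBI therapy is offered. On the other, "Participants with a negative blood transcriptional biomarker and who meet the eligibility criteria for the longitudinal study will be asked to attend follow up" visits every three months for two years. Section 9.1 gives the expected size of the positive group: "we estimate that 15% of these individuals will express the blood transcriptional biomarker at time of recruitment to the study", that is, 150 of 1000.

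The end of Section 5 defines a progressor as someone who converts to biomarker-positive, or reaches an Appendix 6 end point, before two years. Both are described as surrogates for progressive TB. Section 9.2 adds progressors found by linkage to national surveillance records among cross-sectional participants, withdrawals and losses to follow-up. The protocol gives no rate for conversions, Appendix 6 end points or linkage cases.

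**The concern.** The 5% describes active TB in unselected IGRA-positive contacts. The cohort followed is what remains after biomarker-positive contacts have been moved to another part of the study. Section 2 reports that blood signatures of this kind identify people who develop TB within three months. If that is even partly true of the study biomarker, the contacts who remain have a lower active-TB risk than 5%. Section 9.1 adjusts neither the rate nor the denominator.

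The event counted in follow-up is also not the event to which the 5% refers. Appendix 9 expects this follow-up approach to hold the two-year risk of symptomatic TB below 1%, which is fewer than 4 of 400. Most of any 20 progressors would then be surrogate-defined, and the protocol gives no rate for those.

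The number of progressors is the only stated basis for the primary sample size. The design looks for traits present in a subset of progressors, so the count decides how likely it is that 5 of them share a trait.

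**Working it through.** **Inputs from the protocol.** 400 contacts, 5% two-year risk, 15% biomarker-positive at recruitment and the 5-sharer condition (all Section 9.1); eight three-monthly visits (Section 5, Appendix 11).

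**Assumptions.** f, the share of two-year TB progressors already biomarker-positive at entry, is not given and is taken as 0.15 to 0.50. At f = 0.15 the biomarker carries no information about progression. The 15% was estimated for all 1000 participants and is assumed to hold in contacts.

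**Step 1: the plan's own figure.** 400 × 0.05 = 20 and 400 × 0.95 = 380. Both reproduce exactly.

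**Step 2: active-TB progressors among biomarker-negatives.** Their risk is 0.05 × (1 − f)/0.85. Multiply by 400 if 400 are followed after the split, or by 340 (= 400 × 0.85) if 400 are counted before it. The second case reduces to 20 × (1 − f).

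| f | Risk in negatives | 400 followed after split | 400 counted before split |
|---|---|---|---|
| 0.15 | 5.00% | 20.0 | 17.0 |
| 0.25 | 4.41% | 17.6 | 15.0 |
| 0.50 | 2.94% | 11.8 | 10.0 |

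Within this range the count stays at 20 in one cell only: 400 followed after the split, with a biomarker unrelated to progression.

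**Step 3: surrogate conversions.** With conversion probability r per visit and no losses, the two-year proportion is 1 − (1 − r)^8. Setting this to 0.05 gives r = 1 − 0.95^(1/8) = 0.64%. In 400 followed, r = 0.5% gives about 16 converters, 1% about 31 and 2% about 60. These rates are illustrative. They show that the protocol-defined total can fall on either side of 20.

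**Step 4: the 5-sharer condition.** Five sharers are 25% of 20 progressors, 29% of 17, 33% of 15 and 50% of 10. The binomial chance that at least 5 share a trait is:

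| Progressors | Trait in 25% | Trait in 40% |
|---|---|---|
| 20 | 0.585 | 0.949 |
| 17 | 0.426 | 0.874 |
| 15 | 0.314 | 0.783 |
| 10 | 0.078 | 0.367 |

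This is the chance of meeting the condition attached to the power statement. It is not power.

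**Step 5: consistency of the biomarker figures.** If 15% are positive and 5% progress, then even with every progressor positive at entry (f = 1) the two-year positive predictive value could not exceed 0.05/0.15 = 0.33. Section 2 reports 0.99-1 for its signatures. Applied to 60 positives (15% of 400), 0.99 would mean about 59 cases, against 20 expected in all 400.

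**The case against.** The strongest reply is that a shortfall in active TB is not a shortfall in progressors. Section 5 counts biomarker converters and Appendix 6 end points, one of which is two positive symptom answers alone. Section 9.2 adds cases found by linkage. In the order given in Section 5, the biomarker split follows the skin tests and biopsies. Baseline-positive contacts would then already have skin-test profiles, and some who later develop TB might still be captured. This stands. A reader might infer that the planned 20 is too high as a total, but the documents do not support that, because they give no rate for these other sources.

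The reply also holds on the meaning of 400. Section 4 says "400 participants will be recruited to the longitudinal cohort with two year follow up", and Section 12.1 speaks of 400 generating longitudinal data. Both favour 400 actually followed, although Section 9.1 speaks of contacts recruited.

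Three further inferences are tempting and should not be drawn.

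- **That the power above 0.8 is overstated by a known amount.** The claim is openly conditional on 5 sharers and its simulation cannot be checked. Traits shared by fewer than 5 are not shown to be undetectable.
- **That the 15% removed are imminent TB cases.** Section 2 speaks of signatures in general, from unpublished data and under an assumed 5% pre-test probability. Appendix 9 claims only a potential to identify subclinical disease.
- **That f can be derived from the 0.99-1 predictive values.** Step 5 shows that those values cannot hold together with 15% and 5%.

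The reply does not justify the 20 itself. Section 9.1 derives it from active-TB risk, and the possible offsets come from events for which it has no rate.

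**Conclusion.** The mismatch is established: 5% is not the documented rate for the cohort followed, nor for the end point used to classify it. This is an unsupported input and not a slip in multiplication.

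Its size for active TB depends on f and on which 400 is meant. For f of 0.15 to 0.50, expected active-TB progressors are 20 to 11.8 or 17 to 10, given 15% positivity in contacts and no allowance for losses. Keeping 20 requires the favourable reading of 400 and, within that range, a biomarker with no relation to progression, which runs against the study's own rationale.

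The direction and size of any error in the protocol-defined total, and in the power, are not established. If there are fewer progressors, the 5-sharer condition is harder to meet. For a trait present in 25% of progressors, the chance is only 0.585 even at the planned 20.

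**What to change.** Revise Section 9.1 as follows.

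1. State whether 400 counts contacts recruited before the biomarker split or biomarker-negative contacts followed after it.
2. Replace the single 5% and 20 with two expected numbers among biomarker-negatives, one for active-TB progressors and one for surrogate-defined progressors, each with a source or a range.
3. Reconcile the 15% positivity, the 5% two-year risk and the 0.99-1 predictive values in Section 2. Say whether the signatures in Section 2 are the study biomarker.
4. Re-run the existing simulation at about 10, 15 and 20 progressors. Report the power together with the chance of meeting the 5-sharer condition for traits of stated prevalence, for example 25% and 40%.

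The cost is one re-run of an existing simulation and a rewritten paragraph. No extra participants are needed. The stated power may become less favourable.
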